Relationship and sexual satisfaction of stoma patients

18.04.2022

NCT ID: konstanz_001

Study protocol

Relationship and sexual satisfaction of stoma patients – study protocol

18.04.2022

Version 2

Head of study: Dr. med. [name]

deputy: [name]. med. [name]

Table of contents

1. Background	3
2. Aim	3
3. Participants	3
4. Methods	3
5. Statistics	3
6. Protection of data privacy	3
7. Risks	3
8. References	3

1 **Background**

Sexual dysfunctions are common after stoma operations with rectal cancer.¹ Sexual dysfunctions after rectum operations are a known complication.² Patients with stoma have a significantly lower self-esteem compared to healthy people.³ There is no research regarding the connection of a stoma and sexual satisfaction to the best of our knowledge. To advise patients before such an operation it is necessary to investigate such a connection.

2 **Aim**

- Sexual satisfaction of participants with stoma
- Relationship satisfaction of participants with stoma
- Comparing colostomy and ileostomy
- Sensitize people treating patients with stoma

3 **Patients**

Patients with stoma or after having had a stoma are asked to fill out an online questionnaire regarding sexual and relationship satisfaction.

Minimum age: 18 years

No sexual dysfunctions. No disease influencing sexual functioning

4 **Methods**

Anonymous Questionnaire. Retrospective data analysis.

5 **Statistics**

Empiric data analysis of answers and comparing answers to literature.

6 **Protection of data privacy**

Questionnaire is anonymous. Data is only available with password. Only head of study and deputy have access to data.

7 **Risks**

The study is an anonymous questionnaire. The data is analysed retrospectively. So there are no risks for participants.

8 **References**

1. Sutunbuloglu, E., & Vural, F. (2018). Evaluation of sexual satisfaction and function in patients following stoma surgery: A descriptive study. *Sexuality and Disability*, 36(4), 349-361.
2. Hendren, S. K., O'Connor, B. I., Liu, M., Asano, T., Cohen, Z., Swallow, C. J., ... & McLeod, R. S. (2005). Prevalence of male and female sexual dysfunction is high following surgery for rectal cancer. *Annals of surgery*, 242(2), 212.

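### Does the Background's statement that no research exists on stoma and sexual satisfaction undermine the planned comparison with the literature?

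*Protocol*

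**What the plan says.** Section 1 (Background) gives three short statements of prior knowledge, each with a reference, and then says "There is no research regarding the connection of a stoma and sexual satisfaction to the best of our knowledge". The next sentence draws the need for the study from this gap: patients can be advised before surgery only if the connection is investigated.

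Section 8 (References) lists three papers. Reference 1 (2018) is titled "Evaluation of sexual satisfaction and function in patients following stoma surgery: A descriptive study". Reference 3 (2017) is titled "The evaluation of self-esteem and sexual satisfaction of patients with bowel stoma in Turkey". Reference 2 (2005) concerns sexual dysfunction after rectal cancer surgery.

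Section 5 (Statistics) is a single line: "Empiric data analysis of answers and comparing answers to literature". It names no study, population or instrument. Section 2 (Aim) lists sexual satisfaction first, then relationship satisfaction, a colostomy-ileostomy comparison, and raising awareness among those who treat these patients.

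**The concern.** Two things look wrong on a first reading.

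- **Rationale against reference list.** The Background denies that any research exists on a subject that two of its own references name in their titles. The hedge about the authors' own knowledge does not help, because it can cover only papers they have not seen, and they cite both of these just before.
- **Rationale against analysis.** Section 5 relies on "comparing answers to literature". If there were truly no research, the answers on sexual satisfaction would seem to have no comparator. The Background might also lead analysts past the two nearest studies, leaving comparators to be picked once the results are known, or scores to be collected on a scale that cannot be set against published values.

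If both points held, the report would carry a false claim of novelty and the literature comparison would be open to selective choice of sources. A mismatch of scales could not be repaired after data collection.

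**Working it through.** The protocol gives no figure to reproduce here, and no formula applies. The check is to set the sections side by side.

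**Step 1: section 1 against section 8.**

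| Reference | Title names stoma patients | Title names sexual satisfaction | What section 1 cites it for |
|---|---|---|---|
| 1 (2018) | yes | yes | sexual dysfunction: "Sexual dysfunctions are common after stoma operations with rectal cancer" |
| 2 (2005) | no | no: "Prevalence of male and female sexual dysfunction is high following surgery for rectal cancer" | sexual dysfunction as a known complication |
| 3 (2017) | yes | yes | self-esteem: "Patients with stoma have a significantly lower self-esteem compared to healthy people" |

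The count is 2 of 3, or 2/3 = 67%. References 1 and 3 are used for neighbouring facts, and the sexual satisfaction announced in their titles is passed over. The Background sentence therefore conflicts with the reference list. The 67% is only a count of titles. It does not measure an effect on any result.

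**Step 2: section 1 against section 5.** For these two to contradict each other, the literature in section 5 would have to mean earlier research on sexual satisfaction in stoma patients. Section 5 does not say so. Values from healthy people or the general population would fit its wording, could exist even if no stoma research did, and would resemble the comparison with healthy people that section 1 already cites for self-esteem. Section 5 also covers the answers on relationship satisfaction, which the Background sentence does not mention. No contradiction is shown.

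**Step 3: is section 5 the only comparison?** No. Section 2 lists colostomy against ileostomy. That comparison is made within the study's own participants and needs no published comparator.

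**Step 4: would anything change if the sentence were corrected?** Suppose section 1 said that sexual satisfaction after a stoma had already been described in references 1 and 3.

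- The aims in section 2 would stand. Two existing studies, one of which calls itself descriptive and the other of which is confined to Turkey, do not remove the reason to study the question again.
- Eligibility in section 3 and the anonymous questionnaire in section 4 do not depend on the sentence.
- Section 5 would read the same.
- The protocol states no sample size, power, significance level or effect size, so none could rest on it.

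**Step 5: would it help to fix references 1 and 3 now as comparators, and adopt a scale from one of them?** Only their titles are known here. Section 3 of the protocol admits people who no longer have a stoma and excludes those with sexual dysfunction. Whether either paper's population matches that, and which scales they used, cannot be seen. Committing to them unseen could lock in a poor comparison as easily as a good one.

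**The case for a change.** The strongest case for acting is that the sentence is not a side remark. It is absolute, it is refuted by papers the authors cite themselves, and the stated need for the study rests on it, with sexual satisfaction as the first aim. Section 5 is also so brief that nothing in the protocol prevents comparators from being chosen after the answers are in, and a poor choice of questionnaire could not be undone. The remedy would cost about two sentences, plus possible licensing or translation of a scale.

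The first part stands: the sentence is inaccurate. One could read it as meaning that no study has tested the association against people without a stoma, and the titles do not rule that out, but the text does not say it.

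The second part does not stand as a fault of this document. Choosing the comparison sources and the method of comparing scores is detail that a statistical analysis plan commonly holds, and that plan may exist without being shown. Nor is there evidence that the sentence would steer analysts away from references 1 and 3, since both are in the short list before them. The scale argument depends on two unknowns: the instrument of this study, which the protocol does not name, and the instruments of two papers that cannot be seen here.

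**Conclusion.** The Background overstates the gap in the evidence: by title, two of its three references concern the subject it calls unresearched. This is a slip in the rationale, with no consequence for the design or the analysis. The supposed conflict with section 5 is not shown, because the literature there need not be stoma literature and section 2 provides a separate internal comparison. Correcting the sentence would change no aim, population, analysis or error rate, and fixing the two papers as comparators in advance is a debatable trade-off with no demonstrated gain. No change to the plan follows. When the study is written up, the authors can acknowledge references 1 and 3 as earlier work and claim only as much novelty as they can support.

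This conclusion rests on the titles alone for the content of references 1 and 3, and on the possibility that comparison sources and instruments are specified in an analysis plan that is not at hand. If that plan also leaves them open, the gap is one of missing detail in section 5, and rewording the Background would not close it.

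### Is the colostomy–ileostomy comparison undermined because the protocol does not say that the anonymous questionnaire records the reason for the stoma or rectal surgery?

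*Protocol*

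**What the plan says.** Section 2 (Aim) has four bullets: sexual satisfaction, relationship satisfaction, "Comparing colostomy and ileostomy", and raising awareness among those who treat these patients. No hypothesis, effect size or causal claim is attached to the comparison.

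Section 1 (Background) says "Sexual dysfunctions are common after stoma operations with rectal cancer" and "Sexual dysfunctions after rectum operations are a known complication". It ends with the purpose: "To advise patients before such an operation it is necessary to investigate such a connection". The connection meant there, from the preceding sentence, is the one between having a stoma and sexual satisfaction.

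Section 3 (Patients) says "Patients with stoma or after having had a stoma are asked to fill out an online questionnaire regarding sexual and relationship satisfaction". Besides the minimum age of 18 it sets the condition "No sexual dysfunctions. No disease influencing sexual functioning", without saying to which time this refers.

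Section 4 (Methods) reads in full "Anonymous Questionnaire. Retrospective data analysis". Section 5 (Statistics) plans an empirical analysis of the answers and sets them against published work. Section 6 says "Questionnaire is anonymous. Data is only available with password".

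No section lists a single questionnaire item. The reason for the stoma and rectal surgery are not named, and neither is stoma type.

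**The concern.** Colostomy against ileostomy is the only comparison within the study that the protocol names, and the groups are not randomised. The background singles out two factors tied to sexual outcome, rectal cancer and rectal surgery. If these were more frequent with one stoma type and also lowered satisfaction, a crude difference would mix their influence with that of stoma type.

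Usually one would leave this to the statistical analysis plan. Here that answer seems too easy, because no analysis plan can adjust for a variable that was never collected. The survey is anonymous and no link to medical records is described, so an item not asked is lost. A clinician counselling patients ahead of surgery might then read a crude difference as an effect of the stoma type itself.

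**Working it through.** The protocol gives no sample size, standard deviation or effect size, so there is no figure of its own to reproduce. The check is first one of reading, then an illustration with assumed inputs.

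**Does silence mean that the items are absent?** Section 3 gives the topic of the survey, not its contents. The comparison in section 2 cannot be made unless stoma type is asked, yet stoma type is listed nowhere. If an unlisted item counted as an uncollected one, the aim itself would be impossible. The more sensible reading is that the questionnaire is a separate document and the protocol does not reproduce it. It may or may not contain the reason for the stoma and rectal surgery; the text does not settle this.

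**Does the document establish confounding?** Two conditions are needed.

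1. The factor must differ between colostomy and ileostomy respondents. Section 1 says nothing by stoma type.
2. The factor must affect satisfaction. Section 1 links it to dysfunction; the step to satisfaction is an assumption.

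**How large could it be?** All inputs here are assumed. With no true effect of stoma type, the crude difference is (gap in the share with rectal surgery) × (effect of rectal surgery in SD):

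| Gap in share | Effect (SD) | Crude difference (SD) |
|---|---|---|
| 0 | 0.5 | 0 |
| 0.2 | 0.3 | 0.06 |
| 0.4 | 0.5 | 0.20 |
| 0.6 | 0.8 | 0.48 |

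With an assumed n = 100 per group, a two-sided 5% test rejects with probability Φ(b/√(2/n) − 1.96) + Φ(−b/√(2/n) − 1.96), where b is the crude difference. This gives about 7% at b = 0.06, 29% at 0.20 and 92% at 0.48, and 5% at b = 0.

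**What does the section 3 condition do?** If it refers to the time before the operation, these figures stand. If it refers to the time of the survey, take assumed shares of 0.6 and 0.2 with rectal surgery, and dysfunction in 50% after rectal surgery and 20% otherwise.

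- First group: 0.6 × 0.5 + 0.4 × 0.8 = 0.30 + 0.32 = 0.62 remain, so 38% are excluded; share with rectal surgery 0.30/0.62 = 0.484.
- Second group: 0.2 × 0.5 + 0.8 × 0.8 = 0.10 + 0.64 = 0.74 remain, so 26% are excluded; share 0.10/0.74 = 0.135.
- Gap 0.484 − 0.135 = 0.349, hence 0.349 × 0.5 = 0.17 SD instead of 0.20.

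If the effect ran wholly through dysfunction, it would be zero. The second half of the condition, on diseases that influence sexual function, might also remove some rectal cancer patients; its scope is not stated.

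**What would adjustment cost?** With equal groups and an assumed mean share of 0.4, r² = gap² × 0.25/0.24, and the interval widens by the factor √(1/(1 − r²)). For gaps of 0, 0.2, 0.4 and 0.6 the factor is 1.00, 1.02, 1.10 and 1.26, before any gain from explained variance. So adjustment is a trade-off to be weighed when the analysis is planned.

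**The case for a change.** The strongest case for a change is that data collection differs from analysis. A model can be chosen late; an item cannot be added to anonymous answers already given. The protocol itself names the two factors, two or three self-report questions would cost little, and if they are already asked, one sentence would say so.

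The conditional part of this stands: if the items are not asked, they cannot be recovered, and the comparison can then only be reported crude. It is also true that the section 3 condition does not dispose of the matter, since it is undated and does not name rectal surgery.

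The argument does not turn the condition into a fact. It needs the questionnaire to lack the items, the factors to differ by stoma type, and their link to dysfunction to extend to satisfaction; the document shows none of the three. The counselling purpose in section 1 concerns stoma and satisfaction in general, not the choice between stoma types. As written, the aim is met by a descriptive comparison, which analysts would ordinarily present as an association. The low cost also presumes that collection is still open, which the protocol does not say. The undated exclusion is a separate matter between sections 1 and 3 and does not decide this one.

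**Conclusion.** No change to the plan is called for. The protocol makes no false or contradictory statement here; it gives the subject of the questionnaire and leaves its items to the instrument. Recording the reason for the stoma and rectal surgery is a gap that those running the survey can fill sensibly, and stratifying or adjusting is commonly settled in the statistical analysis plan, which is not at hand. The possible distortion cannot be derived from the document; the range of 0 to 0.48 SD rests wholly on assumed shares and effects and includes none at all.

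This rests on two assumptions: that the questionnaire asks stoma type, as the aim requires, and that the comparison is reported descriptively. Should the questionnaire prove to lack the other items, labelling the result an unadjusted association would be enough for the aim as written. The judgement would differ only if the instrument lacked them and the report drew a causal conclusion about stoma type.

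### The exclusion of sexual dysfunction in Section 3 has no time point; taken literally it removes a consequence of the operation and can overstate satisfaction for advice before surgery

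*Protocol*

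**What the plan says.** Section 3 (Patients) defines the survey population: "Patients with stoma or after having had a stoma are asked to fill out an online questionnaire regarding sexual and relationship satisfaction". After a minimum age of 18 it adds: "No sexual dysfunctions. No disease influencing sexual functioning". Neither clause refers to a point in time, and the remaining sections supply none. Section 4 says only that the questionnaire is anonymous and the data analysis retrospective.

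Section 1 (Background) gives the context. It states that "Sexual dysfunctions are common after stoma operations with rectal cancer" and that "Sexual dysfunctions after rectum operations are a known complication". It names the gap to be filled ("There is no research regarding the connection of a stoma and sexual satisfaction to the best of our knowledge") and the intended use: "To advise patients before such an operation it is necessary to investigate such a connection".

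The aims in Section 2 include "Sexual satisfaction of participants with stoma" and "Comparing colostomy and ileostomy". Section 5 plans a descriptive analysis and a comparison with published results.

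**The concern.** Everyone recruited has already had the operation, so eligibility is judged afterwards. A criterion on sexual dysfunction without a time point can then act on something the operation itself caused. Three readings are open:

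- **Literal:** nobody with dysfunction at the survey is eligible, whenever it began. People harmed in this respect by the operation are left out, and the remainder are used to advise people who face the same operation.
- **Pre-existing only:** people with dysfunction before the operation are left out. This selection problem then does not arise, but the text does not say so.
- **Deliberate restriction:** the stoma is to be studied apart from dysfunction. This would be coherent with the gap named in Section 1, but Sections 2 and 3 do not declare it.

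The second clause is equally open. It does not say whether the disease that led to the stoma counts as one that influences sexual functioning. On a strict reading, patients with rectal cancer, the one disease Section 1 names, could be ineligible.

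At stake are the mean satisfaction reported for use before surgery, the colostomy–ileostomy comparison, and the reader's ability to tell which population the results and the literature comparison describe.

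**Working it through.** The protocol states no rate, effect size or sample size for this point, so there is no figure to reproduce. The direction of the bias follows from the text and a two-group mixture; its size needs assumptions.

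**Inputs**

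- p: share of otherwise eligible respondents whose dysfunction arose after the operation. Not in the protocol; assumed 0.2 to 0.6.
- d: satisfaction gap, in SD, between those without and those with such dysfunction. Not in the protocol; assumed 0.3 to 1.0.
- μ0: mean satisfaction of those without dysfunction. It cancels.

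**Overall mean, literal reading**

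- Mean over all otherwise eligible respondents: (1 − p)·μ0 + p·(μ0 − d) = μ0 − p·d.
- Mean over those who remain eligible: μ0.
- Bias: μ0 − (μ0 − p·d) = p·d, upward whenever p and d are both positive.

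| p | d = 0.3 | d = 0.5 | d = 1.0 |
|---|---|---|---|
| 0.2 | 0.06 | 0.10 | 0.20 |
| 0.4 | 0.12 | 0.20 | 0.40 |
| 0.6 | 0.18 | 0.30 | 0.60 |

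Entries are in SD. A smaller share lowers them: p = 0.1 with d = 0.2 gives 0.02 SD. With d = 0 the bias is 0.

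**Colostomy (c) minus ileostomy (i)**

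Each group's mean is raised by its own product, so the difference shifts by p_c·d_c − p_i·d_i.

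- p_c = 0.2, p_i = 0.4, d = 0.5 in both: 0.10 − 0.20 = −0.10 SD. With the shares reversed: +0.10 SD.
- p = 0.4 in both, d_c = 0.3, d_i = 0.5: 0.12 − 0.20 = −0.08 SD.
- Equal products: 0.
- Extremes of the assumed ranges: 0.6 × 1.0 − 0.2 × 0.3 = 0.60 − 0.06 = 0.54 SD, in either direction.

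**If the criterion is applied only in part**

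The product p·d assumes that everyone with dysfunction is excluded, as the text requires. If only a fraction e is excluded, the included mean is μ0 − d·p(1 − e)/(1 − p·e). At p = 0.4, d = 0.5 and an assumed e = 0.5 this is μ0 − 0.5 × 0.20/0.80 = μ0 − 0.125. The bias is then 0.20 − 0.125 = 0.075 SD. For given p and d, p·d is therefore an upper limit, reached when the criterion is followed in full.

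**The case against.** The strongest reply is that this is an ambiguity, not a demonstrated bias. Bias arises on only one of the three readings, and only if dysfunction lowers satisfaction. The document also lends support to a benign reading: Section 1 treats dysfunction as already known and names the link between stoma and satisfaction as the gap, so setting dysfunction aside could be intended. Both statements about dysfunction concern rectal cancer or rectum operations, whereas Section 3 admits any stoma, so p may be lower than assumed. The values of p and d come from outside the document, and the 0.54 SD extreme pairs opposite corners of the assumed grid. Nothing describes how eligibility is verified in an anonymous survey, so exclusion may be incomplete.

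Most of this stands as a limit on size. The bias cannot be estimated from the protocol, it may be small, and it is zero on one reading. What does not follow is that no change is needed. An eligibility criterion is judged by what it says, and followed as written it removes a consequence of the operation. Incomplete screening only describes departure from the written rule. If the restriction is deliberate, the estimate is unbiased for that narrower question, but the aim in Section 2 and the use stated in Section 1 are not limited to it.

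**Conclusion.** The concern holds and should be fixed, with medium confidence. It is certain from the text that the criterion has no time point, that all respondents are assessed after the operation, and that the stated use is advice beforehand. On the literal reading, satisfaction is overstated for that use if dysfunction lowers it. A middle case (p = 0.4, d = 0.5) gives 0.20 SD, within the 0.06 to 0.60 SD spanned by the assumed values. The direction of any shift between colostomy and ileostomy cannot be known from the document. Even where the bias is zero, the protocol leaves the surveyed population undefined.

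**What to change.** Limit both clauses of the criterion in Section 3 to sexual dysfunction or disease present before the stoma operation, other than the disease that led to the stoma. Keep respondents whose dysfunction arose afterwards, and record current dysfunction (yes/no) if the questionnaire does not already do so.

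If excluding current dysfunction is intended, say so in Sections 2 and 3, and limit the conclusions and the literature comparison to stoma patients without sexual dysfunction. If answers have already been collected and no item can be added, state which reading was applied and limit the conclusions accordingly.

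The cost is one eligibility sentence and at most one questionnaire item. Keeping respondents with post-operative dysfunction makes the sample more heterogeneous and relies on recall of status before the stoma. A declared restriction avoids the heterogeneity, but supports advice only about stoma patients without sexual dysfunction.

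### The Section 5 literature comparison cannot be attributed to the stoma, because Section 3 filters on sexual dysfunction at an unstated time and the published samples are unrestricted

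*Protocol*

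**What the plan says.** - **Purpose (Protocol, Section 1).** After noting a lack of research on how a stoma and sexual satisfaction are connected, the protocol states: "To advise patients before such an operation it is necessary to investigate such a connection". The same section says: "Sexual dysfunctions are common after stoma operations with rectal cancer".
- **Aims (Section 2).** These include "Sexual satisfaction of participants with stoma", the matching item for relationship satisfaction, and "Comparing colostomy and ileostomy".
- **Population (Section 3).** "Patients with stoma or after having had a stoma are asked to fill out an online questionnaire regarding sexual and relationship satisfaction". The eligibility filter reads: "No sexual dysfunctions. No disease influencing sexual functioning". No time point is attached to it.
- **Methods (Section 4).** "Anonymous Questionnaire. Retrospective data analysis".
- **Analysis (Section 5).** The whole text is: "Empiric data analysis of answers and comparing answers to literature". It does not say which literature is meant, what kind of sample it should come from, or what the comparison may be used to conclude.

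**The concern.** A person deciding before surgery wants to know what changes with a stoma. That calls for a contrast between stoma and no stoma, or between before and after. Everyone in this survey has or had a stoma, so the published values in Section 5 are the only planned source of such a contrast. The respondents have also been filtered on a condition that the protocol itself links to the operation, while the published samples need not have been.

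Agreement with published values could then be read as showing that a stoma does not matter, and a difference as showing that it does. Either result could instead come from the filter, from a different age and sex mix, from a different instrument, or from who chooses to answer an online questionnaire. A larger sample would remove none of this. The stated use is patient advice, and such a reading could mislead in either direction.

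**Working it through.** The protocol gives no sample size, rate, standard deviation or effect size, so there is no figure of its own to reproduce. The check sets the sections side by side.

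**1. Which contrasts could bear on the Section 1 connection?**
- Colostomy against ileostomy (Section 2): both sides have or had a stoma, so it cannot show stoma against no stoma.
- Current against former stoma: possible within the Section 3 population, but not planned.
- Before against with stoma: no earlier rating is described. The questionnaire is not shown and may contain one.
- Answers against literature (Section 5): planned, and the only remaining candidate.

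**2. What does the filter do under each reading?**
- *At the survey.* Section 1 treats dysfunction as a frequent sequel in the rectal cancer group. Excluding it selects on a consequence of the operation that is closely tied to satisfaction, so part of what a stoma operation may do is removed before analysis.
- *Before the stoma.* This is an ordinary eligibility restriction. The sample is still sexually healthier at baseline than an unfiltered published sample, so a case-mix mismatch remains.

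**3. What does the type of literature change?**
- *Non-stoma samples.* The comparison has the right form, with the mismatch from step 2.
- *Stoma samples.* By their titles, references 1 and 3 concern stoma patients. The comparison is then stoma against stoma and says nothing about stoma against no stoma.

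**4. Illustration of the mechanism. All inputs are assumed and none come from the protocol.** Let q0 be the share with dysfunction in an unfiltered non-stoma reference, q1 the share after a stoma, and d the satisfaction deficit, in SD units, of those with dysfunction. Assume that the stoma acts only through dysfunction, that the filter applies at the survey, and that the published sample is unfiltered. Set the mean of those without dysfunction to 0. Then:
- unfiltered stoma minus reference = −q1·d + q0·d = −(q1 − q0)·d
- filtered stoma minus reference = 0 + q0·d = +q0·d
- shift caused by the filter = q0·d + (q1 − q0)·d = q1·d

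Example with q0 = 0.2, q1 = 0.5, d = 1.0: the unfiltered difference is −(0.5 − 0.2)·1.0 = −0.3 SD, the filtered difference is +0.2 SD, and the shift is 0.5 SD.

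Over q0 = 0.1 to 0.3, q1 = 0.3 to 0.7 and d = 0.5 to 1.0, the unfiltered difference runs from 0 to −0.6 SD, the filtered one from +0.05 to +0.3 SD, and the shift from 0.15 to 0.7 SD. Against an unfiltered stoma sample, the filter alone would produce a difference of q1·d, the same 0.15 to 0.7 SD.

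This shows only that a deficit can be hidden or reversed under these assumptions. It does not estimate the bias in this study. Age and sex mix, instrument and self-selection can add to the bias or offset it.

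**The case against.** The strongest reply is that the protocol makes no inferential claim. Section 1 speaks of a connection, Section 2 lists descriptive aims, and Section 5 states no hypothesis, test or effect estimate. Describing how people with a stoma fare, and how the two stoma types compare, can inform advice before surgery without a no-stoma group. **This stands.** A reader might infer that the study cannot meet its aims, or that the protocol asserts a causal effect. The text supports neither. The fault is the unqualified step from the Section 1 purpose to the Section 5 comparison.

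A second reply is that the choice of comparator, standardisation and limits on interpretation are usual content of an SAP, which is not at hand. **This stands in part.** A missing label alone would be no more than missing detail. But purpose, population, filter and an unrestricted comparator are fixed in the protocol. An SAP can choose better literature, but it cannot bring back respondents whom Section 3 excludes or create a no-stoma group.

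A third reply is that the filter may mean dysfunction present before the stoma, and that the literature may itself be stoma samples. **Both are possible.** A reader might infer that the filter certainly removes postoperative dysfunction. The protocol does not say so, and the more serious mechanism depends on that reading. Neither possibility rescues the comparison: the first leaves a case-mix mismatch, and the second leaves no contrast with people who have no stoma.

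**Conclusion.** The point holds as a mismatch between purpose, population and comparator. As written, neither a difference from published values nor agreement with them can be attributed to the stoma. The mechanism is selection if the filter applies at the survey, and case-mix mismatch if it applies before the stoma.

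The conclusion assumes that the published samples are not filtered in the same way, since Section 5 does not require it. Under a survey-time filter, choosing equally filtered literature would not cure the problem, because both samples would then be conditioned on something the operation can cause.

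Size and direction of the bias cannot be derived from the protocol. A reader might infer from Section 1 that the comparison must make a stoma look harmless. That does not follow, because the filter's timing, the literature and the other differences between samples are all unknown.

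The Section 2 aims remain answerable, with one proviso: under a survey-time filter they describe only people without dysfunction. Severity is minor to moderate.

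**What to change.** 1. **Section 3.** State whether the filter refers to the time before the stoma or to the survey. If it refers to the survey, record dysfunction and report results with and without those respondents instead of excluding them, or restrict the conclusion to people without dysfunction. If collection is closed and these people were turned away, only the restriction is left.
2. **Sections 5 and 1.** Compare only with published samples that used the same instrument. State for each whether it is a stoma or a non-stoma sample and what its exclusions were. Standardise for age and sex where published strata allow. State that the comparison does not estimate an effect of the stoma, and reword the Section 1 purpose to match: describing satisfaction among people with a current or former stoma in order to inform patients.
3. **Optional, only if collection is open and the questionnaire lacks it.** Ask the same items for the period before the stoma. Report the paired difference with a 95% confidence interval as a supporting, non-causal analysis. The downsides are recall bias and mixing with the effects of disease, surgery and time. Former-stoma respondents would recall both periods, so report them separately.

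**Cost.** Items 1 and 2 take a few sentences, a search for suitable published samples and, under a survey-time filter, one recorded item. Item 3 adds a few minutes per respondent. The questionnaire is anonymous, so answers already collected cannot be supplemented.
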